- 3. About how much pain medication have you been using since the initial nerve block? How many doses of Ibuprofen or Tylenol per day for how many days? How many doses of morphine sulfate immediate release or other opioids were taken per day for how many days?
- 4. If you used other forms of pain controllers, what were they and how often and for how long did you use them?
- 5. Have you seen your primary care doctor, pain clinic, emergency department, or other pain management follow-up visits for management of your herpes pain? If so, how many visits have you made?
- 6. What side effects have you had since the nerve block?

1. Subjects:

The study population is Maimonides Medical Center emergency department patients older than 18 years of age presenting with acute herpes zoster patient with characteristic dermatomal vesicular skin lesions within 30 days of initial symptoms.

2. Eligibility Criteria:

The inclusion criteria are patient age over 18 with herpes zoster pain onset within 30 days of characteristic dermatomal herpes zoster rash. The exclusion criteria are allergy to bupivacaine, signs of infection over herpes zoster site, greater than 30 days duration of pain, pain across more than one dermatome and pregnant and/or breastfeeding women.

3. Design:

The primary outcome is the percentage of patients who have significant herpetic pain at 1 month and 3 months after receiving the nerve block. Secondary outcomes measured are pain scores pre-injection, and 1 hour, 1 month, and 3 months post-nerve block. The number of tablets of opioids and other analgesics used after discharge as well as the number of return visits for herpetic pain will also be recorded.

4. Data Collection Procedures:

The numerical verbal rating scale pain score will be recorded by a research staff member at 1 hour after administration of nerve block. The patients will then be called at 1 week, 1 month, and 3 months post nerve block for assessment of NRS as well as number of follow-up visits and amount of analgesics used. A medication track form/log will be given to the patients to help record the amount of medications taken in the first week. The patients will be stratified by age: those under 50, 50-59, 60-69, and 70 and older as well as herpes zoster vaccination status.

5. Sample Size:

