Earlier studies show the incidence of post herpetic neuralgia to be up to 43% in patients who are diagnosed with acute herpes zoster.^[14] We will calculate a sample size required to achieve an α of 5 and power of 80% to detect a clinically relevant reduction in the incidence of PHN from 43% to 10%. We will allow for 10% loss of follow-up.

6. Expected Outcomes:

We expect that patients undergoing ultrasound guided nerve block will have decreased incidence of subacute herpetic neuralgia and PHN. We also expect pain to be well controlled at 1 hour, 1 week, 1 month, and 3 months post nerve block.

7. Adverse Event Reporting:

Side effects of local anesthetics are rare but usually target the central nervous system (numbness, metallic taste, anxiety, visual changes, muscle twitching, seizure, somnolence, coma, respiratory depression) and the cardiovascular system (hypertension or hypotension, tachycardia or bradycardia, ventricular arrhythmias and/or asystole). All adverse and unexpected events will be recorded during the calls in the 3-month follow-up period and reported to the IRB as per hospital policy. Adverse events will also be included in the final publication.

References

- 1. Kim M. O'Connor and Douglas S. Pauw. Herpes Zoster. Medical Clinics of North America. July 1, 2013. 97(4); 503-522.
- 3. Kosuke Kawai, Berhanu G Gebremeskel, Camilo J Acosta. Systematic review of incidence and complications of herpes zoster: towards a global perspective. BMJ Open. 2014 June.
- 4. [name]., and [name]. Postherpetic Neuralgia pathogenesis, Treatment, and Prevention. N Engl J Med. 1996. 333:32-42.
- 5. Robert W. Johnson, Robert H Dworkin. Treatment of herpes zoster and postherpetic neuralgia. BMJ. 2003; 326:748.

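### V.7 places the recording of all adverse events at follow-up calls that start at 1 week, so acute events seen by staff before emergency department discharge are not made study data

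*Protocol*

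**What the plan says.** Three parts of the protocol bear on this.

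- **V.7 (Adverse Event Reporting)** fixes the occasion of recording: "All adverse and unexpected events will be recorded during the calls in the 3-month follow-up period". Reporting to the IRB then follows hospital policy. The section also commits to publication: "Adverse events will also be included in the final publication". It describes what it expects to see: "Side effects of local anesthetics are rare but usually target the central nervous system", followed by cardiovascular effects, namely "hypertension or hypotension, tachycardia or bradycardia, ventricular arrhythmias and/or asystole".
- **V (Study Design)** sets the calls at 1 week, 1 month and 3 months and gives the call script. The sixth and last question is the only one on safety: "What side effects have you had since the nerve block".
- **V.4 (Data Collection Procedures)** describes the one staff contact after the block in the emergency department: "The numerical verbal rating scale pain score will be recorded by a research staff member at 1 hour after administration of nerve block". It describes the calls as being "for assessment of NRS as well as number of follow-up visits and amount of analgesics used". It also provides an aid to memory, for medication only: "A medication track form/log will be given to the patients to help record the amount of medications taken in the first week".

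**The concern.** The acute effects of a local anesthetic that V.7 describes include several that a nurse, physician or monitor is better placed to detect than the patient. The protocol nevertheless names a telephone call, at the earliest a week later, as the place where adverse events are recorded. The patient then becomes the source for events that staff may have seen directly, and the protocol gives staff no place to enter them.

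At stake is the safety result that the protocol undertakes to publish. If the plan is followed as written, an event noted in the emergency department enters that result only if the patient knew of it, remembers it and mentions it.

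**Working it through.** No arithmetic applies: the point does not depend on alpha, power or sample size, and the protocol states no figure to reproduce. The check is to set each data-collection occasion beside what the protocol says is recorded there.

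| Occasion | Recorded, according to the protocol | Adverse events named? |
|---|---|---|
| Before injection | Pain score (V, V.3) | Not applicable |
| 1 hour after the block | Pain score, by research staff (V, V.4) | No |
| 1 hour to discharge | Nothing named | No |
| First week at home | Patient's medication log (V.4) | No |
| Calls at 1 week, 1 month, 3 months | Pain, analgesic use, visits (V, V.4); side effects (question 6, V.7) | Yes |

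**Step 1: first named recording.** The block is at time zero, staff see the patient at 1 hour, and the first occasion on which an adverse event is to be recorded is 1 week. No section sets up an adverse-event form, a record of vital signs or a chart review for the emergency department stay.

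**Step 2: what the call can recover.** Question 6 covers the whole period since the block, so the emergency department stay is inside its window. Taking the effects V.7 lists:

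- *Felt by the patient:* for example metallic taste, numbness, twitching muscles, disturbed vision or anxiety. Recall can capture these, with the usual loss of detail.
- *Seen mainly on measurement or observation:* changes in blood pressure, heart rate or rhythm. A patient who felt nothing and was told nothing cannot report them.
- *Uncertain:* seizure, coma, somnolence and respiratory depression. The patient may or may not have been aware, or may have been told. The protocol does not settle this.

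The exposed part is mainly the second group.

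**Step 3: who would have no record at all.** Question 6 is in the script for every call and always reaches back to the block. A patient missed at 1 week can still report at 1 month or 3 months. Only a patient reached at none of the three calls would have no adverse-event record.

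**Step 4: direction.** Events that staff saw but the patient did not report would be left out, and nothing in the plan offsets this. For acute events before discharge, any error from this source is an under-count.

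**The case against.** The case on the other side has real force.

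- **V.7 does not say that events are recorded only at the calls.** This is true. A reader might infer that recording in the emergency department is excluded, or that events there would certainly go unrecorded. The text supports neither. Case report forms are not shown, and staff may record events anyway. What stands is narrower: V.7 covers all events, names one occasion, and gives staff no duty or place to record sooner.
- **V.4's silence proves little.** Also true. V.4 omits the pre-injection pain score, which V and V.3 require, and it omits side effects from its account of the calls, although question 6 asks for them. The point should therefore rest on what V.7 states, not on V.4 as a complete list.
- **The gap is partly covered.** Conceded in step 2. It would go too far to say that patients could not report the listed effects, or that a patient would be unaware of a seizure or coma.
- **Hospital policy may require documentation.** It may, but the policy is not shown, and the clause in V.7 governs reporting to the IRB rather than entry as study data. It lowers confidence without closing the gap.
- **The 10% loss allowance in V.5.** A reader might take it as the share of patients without safety data. The protocol does not say when loss occurs, and step 3 shows that missing one call is not enough.
- **A percentage for one missed event.** It is tempting to divide one event by the number treated. The protocol gives no final sample size, so the result would only be the reciprocal of an assumed number. It would not measure under-reporting.
- **Safety is neither a primary nor a secondary outcome, and V.7 calls the effects rare.** Both are true, and both limit the weight of the point.

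**Conclusion.** The point holds in a limited form. V.7 assigns the recording of adverse events to telephone calls that begin at 1 week and rely on one open recall question. Nothing in the protocol makes events observed by staff between injection and discharge study data. The published count of acute events, particularly those detected by measurement or observation, could be too low.

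The size of any under-count cannot be computed from the document. It may be small. The pain outcomes do not depend on it.

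The conclusion assumes that the plan is carried out as written and that no unseen form or hospital policy already brings these events into the study data. Because that cannot be checked, confidence is moderate. Severity is minor to should-fix: a data-capture gap in a promised result, closed at little cost. A later analysis plan could not repair it, since analysis cannot recover events that were not recorded.

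**What to change.** Amend V.4 and V.7 as follows.

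1. At the existing 1-hour assessment, for every treated patient, the research staff member records any adverse event since injection that was observed by staff, entered in the chart or reported by the patient.
2. Events already charted between that assessment and emergency department discharge are added to the same form, so that the record covers the whole stay and does not stop at 1 hour.
3. V.7 is reworded to name two occasions of recording: the period from injection to emergency department discharge, and the follow-up calls.
4. Question 6 stays for later events, and IRB reporting stays under hospital policy.

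The cost is a few more lines on the 1-hour form, a look at the existing chart and the amended sentences. No new visit, measurement or clinical rule is involved. Two limits remain: signs that nobody measured or noticed stay uncaptured, and events between discharge and the 1-week call still rest on recall.
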